Subjects' HCV genotype and subtype may be assessed based on the Inno-LiPA 2.0 Assay used by the Central lab, the ARUP Assay for Hepatitis C High-Resolution Genotype by the Central lab and/or from phylogenetic analysis of the full length NS3/4a, NS5A, and/or NS5B sequences performed by AbbVie. If the phylogenetic analysis is available it will be used to determine the subject's HCV genotype and subtype. If it is not available, then the ARUP assay result will be used to determine the subject's HCV genotype and subtype, if available. Finally, if neither the phylogenetic analysis result nor the ARUP assay results are available, then the Inno-LiPA assay results will be used to categorize the subject.

Subjects' baseline fibrosis stage will be assessed by investigator during the screening period and categorized as F0 – F1, F2, F3, or F4.

Baseline Child-Pugh score is determined by the Day 1 assessment of ascites and hepatic encephalopathy along with the baseline values of total bilirubin, serum albumin, and international normalized ratio (INR). The Child-Pugh score is the sum of the point assigned for each of the five observed findings as defined in [Table 7](#).

Table 7. Child-Pugh Classification of Severity of Cirrhosis

Parameter	Points Assigned for Observed Findings		
	1	2	3
Total bilirubin, µmol/L (mg/dL)	< 34.2 (< 2)	34.2 – 51.3 (2 – 3)	> 51.3 (> 3)
Serum albumin, g/L (g/dL)	> 35 (> 3.5)	28 – 35 (2.8 – 3.5)	< 28 (< 2.8)
INR	< 1.7	1.7 – 2.3	> 2.3
Ascites*	None	Slight	Moderate to severe
Hepatic encephalopathy**	None	Grade 1 or 2 (or suppressed with medication)	Grade 3 or 4 (or refractory)

* None.

Slight ascites = Ascites detectable only by ultrasound examination.

Moderate ascites = Ascites manifested by moderate symmetrical distension of the abdomen.

Severe ascites = Large or gross ascites with marked abdominal distension.

** Grade 0: normal consciousness, personality, neurological examination, electroencephalogram.

Grade 1: restless, sleep disturbed, irritable/agitated, tremor, impaired handwriting, 5 cps waves.

Grade 2: lethargic, time-disoriented, inappropriate behavior, asterixis, ataxia, slow triphasic waves.

Grade 3: somnolent, stuporous, place-disoriented, hyperactive reflexes, rigidity, slower waves.

Grade 4: unarousable coma, no personality/behavior, decerebrate, slow 2 to 3 cps delta activity.

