Breakthrough = confirmed HCV RNA \geq LLOQ after HCV RNA < LLOQ during treatment, or confirmed increase from nadir in HCV RNA (two consecutive HCV RNA measurements > 1 log₁₀ IU/mL above nadir) at any time point during treatment. A single breakthrough value (\geq LLOQ or > 1 log₁₀ IU/mL above nadir) followed by lost to follow-up will be considered a breakthrough (i.e., will not require confirmation).

On-treatment virologic failure = breakthrough or failure to suppress during treatment (all on-treatment values of HCV RNA \geq LLOQ) with at least 6 weeks (defined as study drug duration \geq 36 days) of treatment.

RVR (rapid virologic response) = HCV RNA < LLOQ in the Week 4 window.

EOTR (end of treatment response) = HCV RNA < LLOQ in the Week 12 window for subjects receiving 12 weeks of treatment and in the Week 24 window for subjects receiving 24 weeks of treatment.

SVR₄ = HCV RNA < LLOQ in the SVR₄ window (4 weeks after the last actual dose of study drug) without any confirmed quantifiable (\geq LLOQ) post-treatment value during that SVR window.

SVR₁₂ = HCV RNA < LLOQ in the SVR₁₂ window (12 weeks after the last actual dose of study drug) without any confirmed quantifiable (\geq LLOQ) post-treatment value before or during that SVR window.

SVR₂₄ = HCV RNA < LLOQ in the SVR₂₄ window (24 weeks after the last actual dose of study drug) without any confirmed quantifiable (\geq LLOQ) post-treatment value before or during that SVR window.

Relapse₁₂ = confirmed HCV RNA \geq LLOQ between end of treatment and 12 weeks after last actual dose of active study drug (up to and including the SVR₁₂ assessment time point) for a subject with HCV RNA < LLOQ at Final Treatment Visit who completes treatment.

Relapse₂₄ = confirmed HCV RNA \geq LLOQ during SVR₂₄ window among subjects who achieved SVR₁₂ and have data available during the SVR₂₄ window.

Relapse_{late} = confirmed HCV RNA \geq LLOQ at any time after the SVR₂₄ assessment time point for a subject who achieved SVR₂₄ and has post-SVR₂₄ HCV RNA data available.

Relapse_{overall} = confirmed HCV RNA \geq LLOQ between end of treatment and up to and including the last HCV RNA measurement collected in the PT Period for a subject with HCV RNA < LLOQ at Final Treatment Visit who completes treatment. Also, include a summary of **Relapse_{overall}** for subjects who prematurely discontinued treatment (< 77 days for subjects assigned to 12 weeks of treatment and < 154 days for subjects assigned to 24 weeks of treatment).

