For relapse analyses, the completion of treatment is defined as a study drug duration \geq 77 days for subjects assigned to 12 weeks of treatment and \geq 154 days for subjects assigned to 24 weeks of treatment. If the last available post treatment value is \geq LLOQ,

then the subject will be considered a relapse (i.e., will not require confirmation). Relapse analyses will exclude subjects who do not have any post-treatment HCV RNA values.

Reasons for SVR₁₂ Non-Response

Subjects who do not achieve SVR₁₂ (SVR₁₂ non-responders) will be categorized as having:

1. On-treatment virologic failure (see **On-treatment virologic failure** definition);
2. Relapse (defined according to the **Relapse₁₂** definition for subjects who complete treatment);
3. Prematurely discontinued study drug with no on-treatment virologic failure (defined as any SVR₁₂ non-responder who prematurely discontinued study drug (duration < 77 days for subjects assigned to 12 weeks of treatment or duration < 154 days for subjects assigned to 24 weeks of treatment) and did not meet the **On-treatment virologic failure definition**);
4. Missing follow-up data in the SVR₁₂ window (defined as any subject who completed study drug without data in the SVR₁₂ window and not meeting the definitions of [1], [2], or [3]);
5. Other (defined as any SVR₁₂ non-responder not meeting the definitions of [1] – [4], such as a subject with a single quantifiable value within the SVR₁₂ window followed by an undetectable value beyond the SVR₁₂ window).

Reasons for SVR₂₄ Non-Response

Subjects who do not achieve SVR₂₄ (SVR₂₄ non-responders) will be categorized as having:

1. On-treatment virologic failure (see **On-treatment virologic failure** definition);
2. Relapse (defined according to the **Relapse₁₂** definition for subjects who complete treatment);

3. Relapsed after achieving SVR₁₂ (see **Relapse₂₄**);
4. Prematurely discontinued study drug with no on-treatment virologic failure (defined as any SVR₂₄ non-responder who prematurely discontinued study drug and did not meet the **On-treatment virologic failure, Relapse₁₂, or Relapse₂₄** definitions);
5. Missing follow-up data in the SVR₂₄ window (defined as any subject who completed study drug without data in the SVR₂₄ window, and not meeting the definitions of [1], [2], [3], or [4]);
6. Other (defined as any SVR₂₄ non-responder not meeting the definitions of [1] – [5]).

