10.8 Resistance Analyses

If possible, subjects treated with study drug during the Treatment Period who experience virologic failure will have resistance testing conducted if 1) they have on-treatment breakthrough; 2) if they have post-treatment relapse, with a study drug duration ≥ 77 days for subjects assigned to 12 weeks of treatment or with a study drug duration ≥ 154 days for subjects assigned to 24 weeks of treatment; or 3) if they have at least 6 weeks of treatment and fail to suppress by Week 6 (i.e., meet virologic stopping criteria). Subjects meeting one of these criteria will be referred to as subjects in the primary virologic failure (PVF) population, and a listing by subject that includes HCV subgenotype, IL28B genotype, reason for non-response, time point(s) sequenced as closest to time of VF, and HCV RNA value at the VF time point(s) will be produced for these subjects. In addition,

all listings described below will display HCV subgenotype and reason for non-response in the subject identifier for each subject. A separate listing will delineate all subjects in the PVF population for whom no sequencing was performed (e.g., lost to follow-up while HCV RNA \leq 1000 IU/mL).

Only samples with an HCV RNA level of \geq 1000 IU/mL will undergo sequence analysis in order to allow accurate assessment of products of amplification. Therefore if the HCV RNA level at the time of virologic failure (VF) is $<$ 1000 IU/mL, the sample closest in time after the failure with an HCV RNA level \geq 1000 IU/mL will be used if available. If deep sequencing is not performed, clonal sequencing of a given target will be performed only if no variants are detected at signature resistance-associated amino acid positions by population sequencing in that sample. In addition, clonal sequencing may be performed if there is a complex mixture of amino acids at one or more signature resistance-associated position.

The regions of interest for population or deep sequencing from all evaluated time points in this study are those encoding NS3 amino acids 1 – 181, NS5A amino acids 1 – 215, and NS5B amino acids 300 – 581. The prototypic reference sequences used for analysis will be H77 for genotype 1a or Con1 for genotype 1b.

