For each DAA target, resistance-associated signature amino acid variants will be identified by AbbVie Clinical Virology. Amino acid positions where resistance associated variants have been identified in vitro and/or in vivo are 1) for ABT-450: 36, 43, 55, 56, 80, 155, 156, and 168 in NS3 for genotype 1a; 56, 155, 156, and 168 in NS3 for genotype 1b; 2) for ABT-267: 28, 30, 31, 32, 58, and 93 in NS5A for genotype 1a; 28, 29, 30, 31, 32, 58, and 93 in NS5A for genotype 1b; and 3) for ABT-333: 316, 414, 446, 448, 451, 553, 554, 555, 556, 558, 559, and 561 in NS5B for genotype 1a; 316, 368, 411, 414, 445, 448, 553, 556, 558, and 559 in NS5B for genotype 1b. The final list of amino acid positions where resistance-associated variants have been identified will be included in the CSR.

The following definitions will be used in the resistance analyses:

- Baseline variant: a variant (by population or deep sequencing) in a baseline sample determined by comparison of the amino acid sequence of the baseline sample to the appropriate prototypic reference amino acid sequence for a given DAA target (NS3, NS5A, or NS5B).
- Post-baseline variant by population or deep sequencing: an amino acid variant in a post baseline time point sample that was not detected at baseline in the subject and is detectable by population or deep sequencing.
- A post-baseline variant by clonal sequencing: a variant at a signature resistance-associated amino acid position that was not present in a subject by population sequencing at baseline that is detected in a post-baseline sample from that subject by clonal sequencing in at least 2 clones from that sample (among the subset of subjects for whom clonal sequencing is performed) if applicable.
- Emerged variant by population or deep sequencing: a post-baseline variant that is observed in 2 or more subjects of the same subgenotype by population or deep sequencing.
- Linked variant by population or deep sequencing: 2 or more signature resistance associated or emerged amino acid variants identified within a target by population or deep sequencing, and no mixture of amino acids is detected at either position.
- A linked variant by clonal sequencing will be performed: at least 2 clones from a given sample containing the same 2 or more signature resistance-associated amino acid variants by clonal sequencing, if applicable.

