For all subjects, the HCV amino acid sequence as determined by population or deep sequencing at baseline will be compared to the appropriate prototypic reference amino acid sequences. A listing by subject of all baseline variants relative to prototypic reference sequence at signature resistance-associated amino acid positions will be provided for each DAA target (NS3, NS5A, and NS5B).

The following analyses will be performed on the samples from subjects who are in the PVF population and have post-baseline resistance data available.

The HCV amino acid sequence as determined by population or deep sequencing at the time of VF or the sample closest in time after VF with an HCV RNA level of ≥ 1000 IU/mL will be compared to the baseline and appropriate prototypic reference amino acid sequences. A listing by subject and time point of all post-baseline variants detected by population or deep sequencing relative to the baseline amino acid sequences will be provided across all DAA targets (NS3, NS5A, and NS5B).

The number and percentage of subjects with post-baseline variants at signature amino acid positions or emerged variants at non-signature amino acid positions by population or deep sequencing, listed by amino acid position and variant within a DAA target at the time of VF compared to baseline will be summarized, along with the number of subjects within a DAA target and overall. The analyses will be grouped by HCV subgenotype (1a or 1b) and DAA target (NS3, NS5A, or NS5B) and will list the subject numbers of subjects with each variant. The number of subjects with resistance variants in 3 targets, 2 targets or 1 target will be provided.

In addition, a listing by subject and time point of all post-baseline variants (by population or deep sequencing) at signature resistance-associated amino acid positions relative to the appropriate prototypic reference amino acid sequences will be provided.

Linkage between emerged or signature variants by population or deep sequencing will also be evaluated. A listing by subject and time point of the linked variants by population or deep sequencing for each target will be provided.

If clonal sequencing is performed, listings by subject of post-baseline variants by clonal sequencing will be provided for each DAA target. Listings of post-baseline variants by clonal sequencing by subject, amino acid position and variant within a DAA target, and time point will be provided.

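### The relapse definitions run for up to five years with no reinfection category, so a new infection after cure would be reported as relapse

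*SAP*

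**What the plan says.** SAP 10.1 gives three relapse definitions that reach beyond post-treatment Week 12. All depend on HCV RNA at or above the LLOQ after earlier suppression.

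- **Relapse24** applies to subjects who achieved SVR12 and is confined to the SVR24 window, study drug end days 127 to 210 (SAP 6.2, Table 3).
- **Relapse_late** covers confirmed values "at any time after the SVR₂₄ assessment time point for a subject who achieved SVR₂₄" and has no upper time limit.
- **Relapse_overall** covers treatment completers from end of treatment "up to and including the last HCV RNA measurement collected in the PT Period". Premature discontinuers get a separate summary.

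A last available value at or above the LLOQ also counts, without confirmation. HCV RNA is measured at every post-treatment visit to Week 260 (Protocol Table 7). The one exclusion is for values on or after the start of another HCV treatment (SAP 6.3).

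SAP 10.7 tabulates and lists relapse after the SVR24 window and at any post-treatment time. SAP 10.8 admits completers to the primary virologic failure (PVF) population "if they have post-treatment relapse, with a study drug duration" of at least 77 or 154 days, with no limit on when the relapse occurs. A post-baseline variant there is one "that was not detected at baseline in the subject and is detectable by population or deep sequencing".

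Phylogenetic work is planned: SAP 7.1 refers to "phylogenetic analysis of the full length NS3/4a, NS5A, and/or NS5B sequences performed by AbbVie". Its stated use is to assign genotype and subtype, not to tell a returning virus from a new one.

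**The concern.** Quantifiable HCV RNA after cure can mean that the original virus has returned or that the subject has acquired another one. The first is failure of the treatment. The second is neither loss of the original response nor selection by the study drugs. Over five years the second becomes a practical possibility, and none of the eleven exclusion criteria specifically bars continuing exposure risk; criterion 5 is general investigator judgement.

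The SAP's rules cannot separate the two. Followed exactly, they turn a new infection in year 3 into a late relapse. This is a stated rule that gives a wrong classification, not a detail left open. Protocol 3.1 presents the study as the first to follow this regimen's outcomes through five years, so its late-relapse figures are likely to be read as evidence on durability. Deciding which cases are reinfections only after seeing them would be post hoc.

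**Working it through.** **Step 1. Follow a reinfected subject through the rules.** Take a treatment completer who achieved SVR12 and later acquires a new virus.

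| Timing or condition | Reported as | Where |
|---|---|---|
| New viraemia in days 127 to 210 | Relapse24; SVR24 non-response through relapse after SVR12; SVR12/SVR24 discordance | SAP 10.1, 10.7 |
| New viraemia after SVR24 | Relapse_late | SAP 10.1, 10.7 |
| Either | Relapse_overall; PVF population | SAP 10.1, 10.8 |
| Sample of at least 1000 IU/mL sequenced, strain differs from baseline | Post-baseline variants | SAP 10.8 |
| Difference at a non-signature position | Counted as emerged only if seen in two or more subjects of the same subgenotype; not in the persistence tables | SAP 10.8 |
| Difference at a signature position | Signature-variant counts and persistence tables | SAP 10.8 |

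**Step 2. Person-years at risk.** The plan states no figure to reproduce. The inputs are about 600 subjects (SAP 4.2), 4% without SVR12 and dropout up to 20% (SAP 4.3), and follow-up to day 1820 (SAP Table 3).

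- SVR12 subjects: 600 × 0.96 = 576.
- From the end of the SVR24 window: (1820 − 210)/365.25 = 4.41 years; 576 × 4.41 = about 2,540 person-years.
- With 20% exponential dropout over five years: g = −ln(0.8)/5 = 0.0446; 576 × (1 − e^(−0.0446 × 4.41))/0.0446 = about 2,305.
- From nominal Week 24 with no dropout: 576 × 236/52.18 = about 2,605.

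The range is therefore about 2,300 to 2,600.

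**Step 3. Expected reinfections.** The rate is an assumption.

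| Rate per 100 person-years | 2,305 person-years | 2,605 person-years |
|---|---|---|
| 0.1 | 2.3 | 2.6 |
| 0.5 | 11.5 | 13.0 |
| 1.0 | 23.0 | 26.1 |

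Relapse24 alone covers 84 days: 576 × 84/365.25 = about 132 person-years, or 0.1 to 1.3 cases at the same rates.

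**Step 4. Comparison with true relapse** (Protocol 3.0).

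- M11-646: 6 relapses in 322 genotype 1a and 1 in 151 genotype 1b subjects, so 7/473; × 600 = 8.9.
- M13-098: 5/173 and 2/123, all relapses, so 7/296; × 600 = 14.2.

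Reinfections would equal true relapses at a rate between 8.9/2,605 = 0.34 and 14.2/2,305 = 0.62 per 100 person-years. The comparison is rough, because both studies excluded cirrhosis and this one plans 100 to 150 F4 subjects. In the cirrhosis study M13-099, relapse was 12/208 (5.8%) with 12 weeks and 1/172 (0.6%) with 24 weeks.

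**The case against.** The strongest reply is that little depends on these outputs. The objectives are clinical outcomes by SVR12 status, the SVR12 rate, patient-reported outcomes and adherence. Late relapse sits among the additional efficacy analyses, and resistance is descriptive. This stands, and it limits the importance of the point.

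A reader might infer that reinfections would be reported wholesale as treatment-emergent resistance and fill the five-year persistence tables. The documents do not support that. The SAP does not use that term, and the persistence summaries cover signature positions only. Entry to the resistance outputs requires completed treatment, adequate HCV RNA and sequencing, which is planned only where possible. A target with no resistance-associated variant at failure is not sequenced in later samples.

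It may also be said that the cases are not hidden, since first relapses and post-baseline variants are listed by subject. A strongly divergent strain might be noticed there, but the tables would still count it as relapse.

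Finally, the material for the fix is less certain than SAP 10.8 alone suggests. That section says "For all subjects, the HCV amino acid sequence as determined by population or deep sequencing at baseline will be compared" with reference sequences, whereas the protocol synopsis limits resistance information to a subset of virologic failures. SAP 7.1 uses phylogenetic results only if they are available. Some stored baseline samples may therefore need sequencing. Protocol Table 7 collects resistance and archive samples at Day 1 and at post-treatment visits, so the fix remains feasible.

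**Conclusion.** The point holds as a classification error in the late virologic outputs. The affected results are Relapse24, Relapse_late, Relapse_overall, the SVR24 non-response reasons, SVR12/SVR24 concordance, the PVF population and, at signature positions only, the persistence tables.

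The primary analysis and the SVR12 rate are not affected. SVR12 status is settled in days 57 to 126, so a reinfection in a subject who has already achieved SVR12 changes neither that rate nor the groups compared for clinical outcomes.

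The size is about 2 to 26 misclassified cases, against about 9 to 14 true relapses in 600. It rests on the assumed 0.1 to 1.0 per 100 person-years, on 96% SVR12, and on dropout between none and 20%. A reader might go further and infer that late relapse would be mostly reinfection. The documents give neither a reinfection rate nor a late-relapse rate, so that cannot be shown. The missing category is certain; its numerical effect is not. The correction is worth making before the late data are seen.

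**What to change.** Add a rule to SAP 10.1 for HCV RNA at or above the LLOQ after SVR12, based on comparing the recurrence sequence with the subject's own baseline sequence:

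- **Reinfection:** a different genotype or subtype, or failure to cluster phylogenetically with baseline.
- **Relapse:** clustering with baseline.
- **Indeterminate:** no usable sequence.

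Exclude reinfections from Relapse24, Relapse_late, Relapse_overall, the SVR24 non-response reason for relapse after SVR12, and the PVF and persistence populations. List reinfection and indeterminate cases separately. Report relapse twice, with indeterminate cases counted as relapse and then as not relapse.

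The cost is SAP wording and one phylogenetic comparison per recurrent case, with sequencing of the stored baseline sample where that has not been done. No new sampling visit is needed. A few low-titre cases will stay indeterminate.

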10.2 Handling of Multiplicity

No adjustment for multiple comparisons is used in this open-label long-term outcome study.

10.3 Primary Efficacy Analysis

The primary efficacy analysis will be conducted among subjects in the ITT population as described in Section 5.1. HCV RNA values and SVR₁₂ will be imputed as described in Section 6.3.

The primary efficacy endpoint is to assess the effect of response to treatment (as assessed by SVR₁₂ status) on clinical outcomes by comparing the time to incidence of the following events between subjects who achieve SVR₁₂ and those who do not.

- All-cause death
- Liver-related death
- Liver decompensation
- Liver transplantation
- Hepatocellular carcinoma

- Composite of any of the above outcomes

For each of the six event types as listed above, a subject's time to event will be defined as the number of days from the first day of study drug dosing for the subject to the day the subject experiences an event of interest. All events of interest will be included, regardless of whether the event occurred while the subject is still taking study drug or has previously discontinued study drug. If the subject does not experience an event of interest nor has the subject died (all-cause death), the subject's data will be censored at the date of the subject's last available assessment of clinical outcomes. For subjects with no post-baseline assessment, the subject's data will be censored on the first day of study drug dosing. All-cause death is a censoring event for liver-related death, liver decompensation, liver transplantation and hepatocellular carcinoma. Time to the composite of clinical outcomes is the time to the first occurrence of any clinical outcome.

For each of the six event types, the distribution of time to event will be estimated for subjects who have achieved SVR₁₂ and those who haven't using Kaplan-Meier methodology and compared between the subjects who have achieved SVR₁₂ and those who haven't using the log-rank test.

For each of the six event types, the 1-, 2-, 3-, 4-, and 5-year event-free survival rate will be estimated using Kaplan-Meier methodology and a 95% confidence interval will be constructed separately for those who have achieved SVR₁₂ and those who have not. For each of the six event types, a Cox proportional hazards (PH) model will be constructed to include all the baseline characteristics as described in Section 7.1, SVR₁₂ status, and other variables as appropriate.

